2. INTRODUCTION

2.1. Study Rationale

The purpose of this study is to evaluate the safety, tolerability, pharmacokinetics (PK), target engagement (TE) and immunogenicity of a single subcutaneous (SC) dose of GSK3858279 when administered to healthy Caucasian, Chinese and Japanese participants.

The outcomes of this study are intended to support the inclusion of Chinese and Japanese participants in global Ph2/3 studies.

2.2. Background

CCL17, previously known as thymus and activation regulated chemokine (TARC), is a member of the CC-family of chemokines that binds and signals through the G-protein coupled CC-chemokine receptor, CCR4 [Imai, 1996; Imai, 1997]. CCL17 is produced by numerous immune and non-immune cell types. CCR4 is predominantly expressed on Th2 cells but is also present on other immune and non-immune cell types.

CCI

[REDACTED], monoclonal antibody (mAb), binding specifically to the chemokine CCL17. It functionally inhibits CCL17 activating the chemokine receptor CCR4, to prevent downstream consequences of CCR4 signalling.

At the time of this protocol, GSK3858279 is being developed for treatment of osteoarthritis pain. Alleviating chronic pain is a major unmet need, as current therapies (e.g. NSAIDs, opioids) have significant side effects and addiction liabilities that prevent their effective use in treating the patient's pain.

Rationale for CCL17 neutralisation in OA pain has been generated in vivo pre-clinically and inflammatory and arthritis models. CCL17 has been recently identified as a peripheral mediator of inflammatory pain and can itself induce arthritis.

In light of the global COVID-19 pandemic, all participants will be screened for COVID-19 at the beginning of the study and will be required to have a negative SARS-CoV-2 test prior to commencing the study. All participants will also be required to show evidence of complete COVID vaccination to be eligible to participate in the study. Please see further details for risk assessment and mitigation strategy below.

2.3. Benefit/Risk Assessment

More detailed information about the known and expected benefits and risks and reasonably expected adverse events (AEs) of GSK3858279 may be found in the see Investigator's Brochure **CCI** [REDACTED] Effective 02 JUL 2021.

Details of these risks, as well as the risks associated with the procedures, and the proposed strategy to mitigate/monitor these risks are detailed in Section **2.3.1**.

In this study, safety will be monitored closely both by subjective reporting and by objective means, i.e. serial assessments of vital signs, clinical laboratory information and cardiac monitoring. The study will be run in a clinical unit with access to hospital facilities for the treatment of medical emergencies. Participants will remain monitored in the clinic for a minimum of 2 hours after completion of dosing but will remain in the clinic until Day 3 and will only be discharged from the unit if the investigator deems it safe to do so.

2.3.1. Risk Assessment

Potential Risk of Clinical Significance	Summary of Data/Rationale for Risk	Mitigation Strategy
Investigational Product (IP)		
Hypersensitivity, including injection site and infusion reactions CCI	
The administration of any (human) mAb has the potential to induce local or systemic immunologic reactions, for example acute allergic reactions (type I) and immune complex disease (ICD) associated with the formation of anti-drug antibodies (ADA) (type III).
	
Participant Selection: Participants with a history of sensitivity to the study medication, or a history of any drug or other allergy that, in the opinion of the investigator, contraindicates their participation, will not be permitted to enter the study. Participants with renal disorders will also be excluded.
 
Participant monitoring: In Part A of FiH study (207804), participants remained in the inpatient facility for 48 hours post dosing to allow adequate monitoring by trained site personnel.
 
In Part B of FiH (207804) and in this study (212979), participants will be monitored for a minimum of two hours post dosing.
 
Emergency resuscitation facilities will also be available.

Potential Risk of Clinical Significance	Summary of Data/Rationale for Risk	Mitigation Strategy
	CCI	Participants will be instructed in the Informed Consent Form (ICF) as to the signs and symptoms of hypersensitivity reactions and be instructed to seek immediate clinical care should they develop.
Immunogenicity		Samples will be drawn at baseline and at regular intervals to test for immunogenicity, and participants will be monitored for any evidence of adverse reaction as detailed in the hypersensitivity section of this table. Clinical laboratory safety assessments are included in the study. Urine microscopy and laboratory quantification of proteinuria will be investigated following unexplained dipstick proteinuria or haematuria.

Potential Risk of Clinical Significance	Summary of Data/Rationale for Risk	Mitigation Strategy
	CCI [REDACTED]	
Risk of Infection	
The intended pharmacologic effect of GSK3858279 may result in an CCI [REDACTED] [REDACTED]. CCI [REDACTED]
	
Participant Selection Participants with active or chronic infections or a history of recent or recurrent infections will not be included in the study – see Section 5.1.
 
Participant Monitoring Participants will be monitored for infection. Participants will be instructed in the ICF as to the signs and symptoms of infection, and to contact the site personnel should they develop.

Potential Risk of Clinical Significance	Summary of Data/Rationale for Risk	Mitigation Strategy
	CCI	
Vaccination Reactions		
Participant selection and non-permitted medications:
 
Attenuated live vaccines should not be administered to participants within 30 days prior to dosing and for five half-lives after dosing. If indicated, non-live vaccines (e.g. inactivated influenza vaccines) may be administered whilst receiving GSK3858279 based on an assessment of the benefit:risk (e.g. risk of decreased responsiveness).

Cardiac Risks		
Participant Exclusion: Participants with a history of cardiac disease or cardiac abnormalities (including abnormal Troponin I and NT-proBNP) that, in the opinion of the investigator, would compromise cardiac safety will be excluded from the study.
 
Participant monitoring: Investigations during screening include ECG,

Potential Risk of Clinical Significance	Summary of Data/Rationale for Risk	Mitigation Strategy
	CCI	echocardiogram and troponin I and NT-proBNP. Troponin I and NT-proBNP will be monitored after dosing.
Bleeding Risk	CCI	Participant exclusion and non-permitted medication Participants with a previous or current history of bleeding diathesis will be excluded.

Potential Risk of Clinical Significance	Summary of Data/Rationale for Risk	Mitigation Strategy
	CC1	Use of anti-coagulants or anti-platelet agents will be prohibited.
Skin Reactions		Participant Exclusion Participants with a history of drug-induced skin reactions and Stevens-Johnson Syndrome will be excluded. Participant Monitoring Clinically significant skin reactions will be reviewed by a dermatologist and, if appropriate, a skin biopsy will be requested for histological analysis.

Potential Risk of Clinical Significance	Summary of Data/Rationale for Risk	Mitigation Strategy
	
Clinical
 
There were no reports of any clinically significant skin reactions during Part A of the FiH study (207804) in healthy participants.
	
Study Procedures		
Risk associated with blood draws	Fainting, mild pain, bruising, irritation or redness at phlebotomy site, may be associated with blood draws.	Experienced site staff will follow standard approaches for managing events related to blood draws
Other		
SARS-CoV-2	
The current SARS-CoV-2 pandemic can pose a challenge to integrity of the trials, protection of participants' rights, safety and wellbeing and the safety of clinical trial staff. Therefore, risk mitigation strategies will be put in place for this trial and will be evaluated on an ongoing basis for the duration of this trial, or until there is a consensus that the period of the SARS-CoV-2 outbreak in the Australia has passed. If the dynamics of the SARS-CoV-2 outbreak change in such a way that the safety of the trial participants and clinical trial staff or integrity of the data collected during this clinical trial cannot be guaranteed, the trial will be halted.
 
CC1
	
Participant selection and monitoring
 
Healthy subjects in the current study fall in a low risk category for complications of COVID-19, the disease caused by the SARS-CoV-2 virus. To reduce the risk of SARS-CoV-2 infections among trial participants, measures and procedures based on the advice issued by GSK Global COVID Guidance should be followed. These would include but are not limited to counselling participants regarding the importance of infection control measures such as hand washing, reducing inter-personal contacts as much as possible and participant awareness of potential COVID-19 symptoms.

Potential Risk of Clinical Significance	Summary of Data/Rationale for Risk	Mitigation Strategy
	CCI	
Participants must also show evidence of complete COVID-19 vaccination to be eligible to participate in the study
 
Site trial staff in direct contact may receive additional protection via the use of Personal Protective Equipment (PPE) and disinfectants as per local guidance.
 
All trial subjects will be screened for SARS-CoV-2 with a PCR or lateral flow test:
 
 1) at initial screening 2) prior to admission to the clinical unit and 3) in case of symptoms possibly related to COVID-19 
Protection of Trial Integrity Adherence to the protocol protects the integrity of the data collected during this clinical trial, as well as participants' data protection rights.

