2.3.2. Benefit Assessment

There will be no direct benefit to the healthy participants in this study. However, participants will undergo a medical evaluation during screening (including physical examination, electrocardiogram (ECG), vital signs and laboratory assessments), which may provide important health information. The information obtained in this study will inform the conduct of future clinical studies to contribute to the process of developing new therapies for diseases such as Osteoarthritis where there is high unmet medical need.

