2.3.3. Overall Benefit: Risk Conclusion

The safety of each individual participant has been prioritised and the eligibility, monitoring, enhanced monitoring and study level stopping criteria described in Section 7 have been designed to minimise risks to participants associated with exposure to GSK3858279. However, participants will undergo a medical evaluation during screening (including physical examination, electrocardiogram (ECG), vital signs and laboratory assessments), which may provide important health information. Taking into account these measures designed to minimise risks, the potential risks identified in association with GSK3858279 are justified.

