5. STUDY POPULATION

Prospective approval of protocol deviations to recruitment and enrolment criteria, also known as protocol waivers or exemptions, is not permitted.

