5.1. Inclusion Criteria

Participants are eligible to be included in the study only if all of the following criteria apply:

TYPE OF PARTICIPANT AND DISEASE CHARACTERISTICS	
1. Participants who are overtly healthy as determined by medical evaluation including medical history, physical examination, laboratory tests and cardiac monitoring [12-lead ECGs].	A participant with a clinical abnormality or laboratory parameter(s) outside of the reference range for the population being studied that is not specifically listed in the inclusion or exclusion criteria may be included if the Investigator (in consultation with the GSK Medical Monitor if required) agrees and documents that the finding is unlikely to introduce additional risk factors and will not interfere with the study procedures or interpretation.
AGE	
2. Between 20 and 65 years of age inclusive, at the time of signing the informed consent.	
INFORMED CONSENT	
3. Capable of giving signed informed consent which includes compliance with the requirements and restrictions listed in the informed consent form (ICF) and in this protocol.	
COVID-19 (SARS CoV-2) Vaccination	
4. Participants who have evidence of completed vaccination for SARS-CoV-2 with an approved vaccine	
WEIGHT	
5. Body weight within the range 45 – 100 kg and body mass index (BMI) within the range 18-29.9 kg/m ² (inclusive) for Chinese and Japanese participants. Caucasian participants must exhibit BMI range of 18 – 32.0 kg/m ² .	
GEOGRAPHICAL ANCESTRY	
6. Japanese Participants are eligible based on meeting all of the following:	

 • Participants born in Japan • Descendants of four ethnic Japanese grandparents and two ethnic Japanese parents • Have lived outside Japan for less than 10 years at the time of screening 	
7. Chinese Participants are eligible based on meeting all of the following:	

- Participant born in mainland China, Hong Kong or Taiwan
- Descendants of four ethnic Chinese grandparents and two ethnic Chinese parents
- Have lived outside mainland China, Hong Kong or Taiwan for less than 10 years at the time of screening
- 8. Caucasian Participants are eligible based on meeting the following:
- Declaration of familial Caucasian/European ancestry (having 2 parents of Caucasian/European ancestry and 4 grandparents of Caucasian/European ancestry)

SEX**9. Male or female participant:****a. Male participants:**

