5.2. Exclusion Criteria

Participants are excluded from the study if any of the following criteria apply:

MEDICAL CONDITIONS

1. History or presence of cardiovascular, respiratory, hepatic, renal, gastrointestinal, endocrine, haematological, or neurological disorders capable of significantly altering the absorption, metabolism, or elimination of drugs; constituting a risk when taking the study intervention; or interfering with the interpretation of data.
 
2. Personal or family history of cardiomyopathy.
 
3. Abnormal blood pressure at screening as determined by the investigator.
 
4. History of symptomatic herpes zoster
 
5. Evidence of active or latent tuberculosis (TB) as documented by medical history, examination, and TB testing with a positive (not indeterminate) QuantiFERON test.
 
NOTE: In cases where the QuantiFERON test is indeterminate, the participant may have the test repeated once, but they will not be eligible for the study unless the second test is negative. In cases where the QuantiFERON test is positive, the participant should be followed up as per standard of care. If a locally-read follow up chest x-ray shows no evidence of current or previous pulmonary tuberculosis, the participant may be eligible for the study at the discretion of the Investigator and GSK Medical Monitor.
 
6. Significant allergies to humanized monoclonal antibodies as per principal investigator's and GSK medical monitor's judgements.
 
7. History or evidence of clinically significant multiple or severe drug allergies, intolerance to topical corticosteroids, or severe post-treatment hypersensitivity reactions (including, but not limited to, erythema multiforme major, linear immunoglobulin A (IgA) dermatosis, toxic epidermal necrolysis, and exfoliative dermatitis)
 
8. History of lymphoma, leukaemia, or any malignancy within the last 5 years except for basal cell or squamous epithelial carcinomas of the skin that have been resected with no evidence of metastatic disease for 3 years.
 
9. Alanine transaminase (ALT) $>1.5 \times$ upper limit of normal (ULN)
 
10. Bilirubin $>1.5 \times$ULN (isolated bilirubin $>1.5 \times$ULN is acceptable if bilirubin is fractionated and direct bilirubin $<35\%$).
 
11. Current or chronic history of liver disease, or known hepatic or biliary abnormalities (with the exception of Gilbert's syndrome or asymptomatic gallstones)
 
12. Corrected QT (QTc) >450 msec
 
NOTES:

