
- The QTc is the QT interval corrected for heart rate according to Bazett's formula (QTcB), Fridericia's formula (QTcF), and/or another method, machine-read or manually over-read.
- The specific formula that will be used to determine eligibility and discontinuation for an individual participant should be determined prior to initiation of the study. In other words, several different formulae cannot be used to calculate the QTc for an individual participant and then the lowest QTc value used to include or discontinue the participant from the trial.
- For purposes of data analysis, QTcF, another QT correction formula, or a composite of available values of QTc will be used as specified in the Reporting and Analysis Plan (RAP).

13. History of Stevens Johnson Syndrome
14. Known immunodeficiency
15. Participants with a chronic infection (e.g., osteomyelitis), who have been receiving treatment within three months prior to dosing or individuals with an active infection.
16. Previous or current history of bleeding diathesis, excessive bleeding or coagulation disorders
17. History of significant medical illness in the opinion of the investigator would interfere with the study procedures and / or assessments

PRIOR/CONCOMITANT THERAPY

18. Intended use of over-the-counter or prescription medication including herbal medications within 7 days prior to dosing (or 14 days if the drug is a potential enzyme inducer) or 5 half-lives (whichever is longer) before the start of study intervention until completion of the follow-up visit, unless, in the opinion of the investigator and sponsor, the medication will not interfere with the study.
19. Live vaccine(s) or plans to receive such vaccines within 1 month of screening until final follow-up visit.
20. Treatment with biologic agents (such as monoclonal antibodies including marketed drugs) within 3 months or 5 half-lives (whichever is longer) prior to dosing
21. Treatment with antiplatelet or anticoagulant agents within 7 days of dosing
22. Major surgery (as per investigator's judgement) within 3 months prior to dosing

PRIOR/CONCURRENT CLINICAL STUDY EXPERIENCE

23. Participation in the study would result in loss of blood or blood products in excess of 500 mL within 3 months.

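### Protocol 2.3.1 says recent or recurrent infection is excluded, but no criterion in 5.1 or 5.2 names it, and criterion 15 covers chronic infection only if treated within three months

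*Protocol*

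**What the plan says.** Protocol 2.3.1, Risk of Infection row, under participant selection: "Participants with active or chronic infections or a history of recent or recurrent infections will not be included in the study". The sentence carries no opinion qualifier and points to 5.1.

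Protocol 5.1 has no criterion on infection history. Its nearest items are inclusion 1, "Participants who are overtly healthy as determined by medical evaluation including medical history, physical examination, laboratory tests and cardiac monitoring", and inclusion 4, completed SARS-CoV-2 vaccination.

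Protocol 5.2, criterion 15, is the only general infection criterion: "Participants with a chronic infection (e.g., osteomyelitis), who have been receiving treatment within three months prior to dosing or individuals with an active infection".

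Section 5 adds: "Prospective approval of protocol deviations to recruitment and enrolment criteria, also known as protocol waivers or exemptions, is not permitted".

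The risk section ends, in 2.3.3, by relying on eligibility and monitoring: "Taking into account these measures designed to minimise risks, the potential risks identified in association with GSK3858279 are justified". Section 2.3.2 says of the same people: "There will be no direct benefit to the healthy participants in this study".

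**The concern.** Sites enrol on the numbered criteria. When a risk table promises an exclusion that those criteria do not contain, an ethics committee or regulator reading 2.3.1 credits the study with a protection that screening may not deliver.

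Infection is listed in 2.3.1 as a risk, and the visible text links it to the drug's intended pharmacology. Study treatment is one dose given as four injections on one day, so exposure cannot be withdrawn once dosing is complete. At stake is an avoidable exposure of healthy volunteers, and a benefit-risk statement that rests partly on a measure not fully put into operation.

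**Working it through.** No arithmetic beyond counting applies. The check sets each infection category in 2.3.1 against every criterion in 5.1 and 5.2.

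| Category in 2.3.1 | General criterion that names it | What else can reach it |
|---|---|---|
| Active | Exclusion 15, in full | Clinical status re-check before dosing (Schedule of Activities) |
| Chronic | Exclusion 15, only if treated within three months before dosing | TB (5), hepatitis B and C (26 to 29), HIV (33); otherwise discretion |
| Recent, resolved | None | Medication washout (18); discretion |
| Recurrent | None | Zoster history (4); immunodeficiency (14); discretion |

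**Counts.** Exclusion criteria concerning infection are 4, 5, 15, 26, 27, 28, 29, 33 and 34, which is 9 of 37. Criterion 14 concerns susceptibility to infection; adding it gives 10 of 37. On either count, the number naming recent or recurrent infection in general is 0.

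**Do the general clauses close the gap?**

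- Inclusion 1 accepts an unlisted abnormality only if the investigator documents that it is unlikely to add risk. This is a real safeguard, but a resolved infection with normal findings need not count as an abnormality.
- Exclusion 1 covers disorders of named organ systems that would pose a risk with the study drug. Recurrent respiratory or renal-tract infection could be placed there at the investigator's discretion. Skin is not among the systems listed.
- Exclusion 14 requires known immunodeficiency, which a history of recurrent infection does not by itself establish.
- Exclusion 17 turns on interference with study procedures or assessments, not on infection risk.
- Exclusion 18 is a washout of 7 days, 14 days for enzyme inducers, or 5 half-lives if longer. Investigator and sponsor opinion can set it aside. It misses untreated infections and courses finished before the window.

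**Example.** A volunteer whose infection was treated and resolved before the washout window, with normal screening results and no immunodeficiency, breaches none of the 37 exclusions unless the investigator chooses to apply a discretionary one. Section 2.3.1 says this person, having a recent infection, is not to be included.

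**How other rows of 2.3.1 are handled.** The Hypersensitivity and Cardiac rows say expressly that the investigator's opinion decides. The Bleeding row's history exclusion is carried into criterion 16. The Infection row is categorical, like Bleeding, but is only partly carried over. That pattern fits an omission better than a deliberate choice, although it does not prove one.

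**Upper bound on exposure.** Active: 3 cohorts × 7 = 21 planned. Placebo: 3 × 3 = 9 planned.

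**The case against.** The strongest reply is that this is a wording mismatch between a risk summary and the eligibility list. Investigators are told in the same protocol that infection is a risk, and several criteria let them act on it. Haematology is done at screening and on Day -1, clinical status is re-checked before the dose, and active infection is excluded outright. All of that stands. What remains uncovered is a resolved recent infection, a history of recurrent infection, or an inactive, untreated chronic infection, in someone who otherwise looks healthy.

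A second reply is that 2.3.1 could be narrowed to match 5.2. That would make the text consistent, and because part of the infection rationale is redacted, the documents do not show which version the sponsor intended. But it would achieve consistency by dropping a stated safety measure for people who gain nothing directly from the study.

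A reader might infer three stronger things that the documents do not support.

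- That such an enrolment would leave no recorded deviation. Section 2.3.1 is itself protocol text, 10.1.8 has monitors check conduct against the approved protocol, and SAP 6.1.3 does not limit deviations to numbered criteria. Whether one would be recorded is not established either way.
- That about 21 people are at risk from the gap. That is the whole planned active group, not an estimate of the number affected.
- That the Skin Reactions row shows an equal gap needing its own exclusion. It says "Participants with a history of drug-induced skin reactions and Stevens-Johnson Syndrome will be excluded", and its wording is broader than 5.2. But criterion 7 covers multiple or severe drug allergy and "severe post-treatment hypersensitivity reactions (including, but not limited to, erythema multiforme major, linear immunoglobulin A (IgA) dermatosis, toxic epidermal necrolysis, and exfoliative dermatitis"), criterion 13 covers Stevens-Johnson Syndrome, and criterion 37 leaves other drug allergy to opinion, as the Hypersensitivity row also does. Part A of the first-in-human study had no clinically significant skin reactions. A flat exclusion would bar anyone with a single mild drug rash at any time in life.

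**Conclusion.** The infection point holds. Section 2.3.1 promises four exclusions without qualification. Criterion 15 delivers one fully, one partly and two not at all, and the cross-reference leads to a section with no infection-history criterion. Correct use of 5.1 and 5.2 can therefore admit a volunteer whom the stated mitigation rules out.

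The size in participants is unknown: somewhere from zero up to the planned active group of about 21. No harm is alleged. Endpoints, analysis sets, blinding, sample size and analysis are untouched. The conclusion assumes that sites screen from the numbered criteria and that the discretionary clauses may or may not be applied to an infection history. It does not depend on redacted text. It is worth correcting because it is a stated safety measure and the correction is cheap.

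**What to change.** 1. Reword criterion 15 as: *Active or chronic infection, a history of recurrent infection, or a clinically significant infection within three months prior to dosing.* The three months is borrowed from the present criterion 15, where it concerns treatment of chronic infection, so the sponsor should confirm it. The sponsor should also define recurrent by a number of episodes over a period.
2. Put the same wording in the Infection row of 2.3.1. Otherwise that row, which has no window and no significance threshold, would still be broader than 5.2.
3. Change the cross-reference in that row from 5.1 to 5.2.
4. State that the note to criterion 5 still governs its own case. It lets a participant with a positive QuantiFERON and a clear chest x-ray be considered, and a general bar on chronic infection could be read as contradicting it.
5. Add no skin-reaction criterion. At most, qualify the Skin row of 2.3.1 to match criteria 7, 13 and 37.

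The cost is one reworded criterion and matching text in the next amendment, plus a few more screen failures, the number of which the documents do not allow one to estimate. Both amendments so far widened eligibility to help recruitment (Caucasian BMI, Chinese ancestry), and this pulls slightly the other way. The words *clinically significant* keep some investigator discretion, but tie it to a named condition and a fixed window.
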